Specific hypotheses: *Hypotheses 1.1 and 2.1 (neuropsychiatric outcomes)*. Following DAA therapy and obtaining a sustained viral response (SVR), 1.1: participants will show improved neuropsychiatric outcomes (e.g., cognitive function, fatigue, mood), as compared to baseline (pre-DAA therapy). 2.1: participants without AUDs will show greater improvement in neuropsychiatric outcomes than participants with AUDs. *Hypothesis 1.2 and 2.2 (neuroimaging outcomes)*. Reduced fractional anisotropy (FA) will be observed in the tracts that connect regions between which there is decreased functional connectivity. 1.2 and 2.2: Disintegrity within white matter tracks [as measured by FA and mean diffusivity (MD)] observed at baseline visits will be improved following DAA therapy, with greater improvement observed in participants without AUDs. On the fMRI Balloon analogue risk task (BART) and Monetary incentive delay task (MID), adults with HCV will be significantly more likely to display more impulsivity during the baseline visit, as compared to the post-DAA therapy visit. It is hypothesized that AUD may attenuate the positive antiviral therapy effects on impulsivity. *Hypothesis 1.3 and 2.3 (immune activation profile)*. Inflammatory profiles will be associated with neuropsychiatric impairments and alterations in white matter integrity and cortical activity. Following DAA therapy and obtaining an SVR, 1.3: participants will show reduced immune activation profiles (i.e., restored T cell phenotypes and a reduced inflammatory profile), as compared to baseline, and 2.3: participants without AUDs will show greater a reduction in inflammatory factors than participants with AUDs.

Scientific Rationale and Significance

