Comparison groups of adults with: i) active AUD and no HCV (n = 30) and ii) no AUD or HCV (n = 30) will also be studied. Thus, we will enroll 120 participants into the following four study groups: 1) AUD+/HCV+, 2) AUD-/HCV+, 3) AUD+/HCV- and 4) AUD-/HCV-. Evaluations will incorporate neuropsychiatric assessments, brain imaging [resting state (rs) magnetic rsMRI, functional (f) MRI (fMRI), and diffusion tensor imaging], and laboratory methods [e.g., multicolor flow cytometry, quantitative polymerase chain reaction (PCR), and multiplex immunoassays] to assess the interactive effects of alcohol use on brain and immune function [e.g. changes in T cell response and inflammatory cytokines, such as TNF- α] that contribute to viral persistence and neuropsychiatric impairments. We will use general linear models to assess whether average change in the response (e.g., neuropsychiatric and immunologic outcomes) over six months between post- and pre-DAA therapy for each subject differs among the four groups—either due to AUD, HCV, or the potential interaction of these factors—after controlling for other subject-level covariates that remain constant (or nearly so) over the 6 months (e.g., age, sex). Variables that could meaningfully vary over time (e.g., TLFB score) will be summarized in terms of a difference and then included as a covariate.

Table 1. Overview of human subjects procedures, including research visits and HCV treatment schedule^a (as per standard of care)

Weeks					
-2	0	12	18	24	26
Baseline visits (wks -2-0)^c		DAA therapy completion (wk 12)	- Check-in w/participants ^b	SVR assessment (wk 24; 12-wk post DAA therapy)	
- Clinical interview		ETR assessment (wk 12)		6-month follow-up visits (wks 24-26)^c	
- Neuropsychiatric assessment		- Check-in w/participants ^b		- Neuropsychiatric assessment	
- Specimen collection				- Specimen collection	
- Neuroimaging evaluation		DAA therapy initiation (wk 0)		- Neuroimaging evaluation	

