potential interaction of these factors—after possibly controlling for other subject-level covariates that remain constant (or nearly so) over the six months (e.g., age, sex, HCV genotype). Variables that could meaningfully vary over time (e.g., TFLB score, CIWA-Ar score) will be summarized in terms of a difference and then included as a covariate. Number of DAA therapy provider contacts will be included as an extra covariate that counts total contacts. All models will use “robust” (sandwich estimators) of variance to guard against potential misspecification of the underlying distribution of change scores or due to non-constant variance among the groups (Long and Ervin, 2000). The AUD \times HCV interaction will be assessed first in all models fit, and will be removed from the model only if evidence suggests ($p > 0.10$) these two factors don’t modify one another; otherwise, subsequent comparisons of each separate effect will be made within each level of the other (e.g., effect of HCV separately characterized for those with and then without AUD).

A supervised and directed approach will be taken in the exploratory analysis of inflammatory biomarkers. Principal component analysis (PCA) will be used to reduce the collection of ~12 correlated immune factors to a smaller number of uncorrelated linear combinations (the principal components) of biomarkers [e.g., (Bowman et al., 2012)]. Each component of this reduced set of uncorrelated patterns of inflammatory expression will be subjected to the same general linear models described earlier to determine whether AUD, HCV or AUD \times HCV are associated with it, even after adjustment for other covariates. If the overall test of association in the linear model shows significant ($p < 0.10$, for initial screen) variation among the groups, then separate models will be conducted on those biomarkers that most heavily contribute/dominate the principal component being screened. In this way, we may identify combinations of markers that are sensitive to AUD and HCV treatment outcomes, particularly CNS function.

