Power. We estimated group size using fmripower (Mumford and Nichols, 2008). The MATLAB-based program calculates a power estimate given the between-group and within-subject error terms associated with a two tailed t-test of regression coefficients. The results suggested that 30 subjects (male and female) per group would yield a power of 0.8 for the test comparison. This sample size yields an 80% chance for us to identify AUD \times HCV interaction effects of 0.91 standard deviation (SD) or larger at the 0.10 level of significance. Use of the higher alpha-level is done to lessen the chance of making a type II (overlook) error and mistakenly omitting this term from the model. We also have 80% power for a 0.05-level test to detect any main effect, for either AUD or for HCV, of at least 0.51 SD in size. **Table 2** shows the smallest average change (between post- and pre-DAA therapy) among groups that would be of practical interest and the subsequent main effects (AUD+ vs AUD-; HCV+ vs HCV-) and interactions that derive from these minimally relevant average changes. The anticipated SD for the change scores was derived from reported SDs of each outcome supported by literature, and then converted to a SD for the difference assuming a modest correlation of 0.60 between pre- and post-DAA responses within the same subject. The principal comparisons proposed in this work parallel those in our preliminary work, and we were able to readily demonstrate differences in planned comparisons between the groups. Therefore, the proposed 30 subjects per group should provide us with sufficient power to test the predictions, anticipating that a small number of participants with HCV may not achieve SVR (n = ~3-6).

Table 2. Statistical power to evaluate antiviral therapy outcomes of significant clinical impact

Response/outcome	SD(diff)	Treatment group ^a			Effects and Power ^b			
		AUD-/HCV-	AUD-/HCV+	AUD+/HC V-	AUD+/HCV+	AUD main	HCV main	Interact.
Cognitive performance^c								
Attention	2.25	3.5	3.7	1.2	3.5	-1.25 (0.85)	1.25 (0.85)	2.1 (0.81)
Memory	2.50	3.0	3.4	0.4	3.0	-1.50 (0.91)	1.50 (0.91)	2.2 (0.78)
Executive function	1.80	2.0	2.1	0.3	2.0	-0.90 (0.78)	0.90 (0.78)	1.6 (0.78)
Behavioral response								
Impulsivity (BART/MID) ^d	1.35	0	-0.2	-0.1	-1.5	-0.70 (0.80)	-0.80 (0.90)	-1.20 (0.78)
Alcohol use (TLFB)	18.9	0	-1.0	-18	-36	-26.5 (0.99)	-9.50 (0.78)	-17.0 (0.79)
Mental health								
Depression (BDI)	4.0	0	-3.5	-2.7	-11.0	-5.1 (0.99)	-5.9 (0.99)	-4.8 (0.94)

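### The neuropsychiatric and laboratory models condition on concurrent change in TLFB drinking, itself a primary outcome, and no model without it is stated, although Table 2 and Hypothesis 2.1 concern unconditional group differences

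*Combined protocol and SAP*

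**What the plan says.** The rule appears twice. The Overview under Research Design and Methods says: "Variables that could meaningfully vary over time (e.g., TLFB score) will be summarized in terms of a difference and then included as a covariate". The paragraph on neuropsychiatric and laboratory measures, under Statistical analyses and power, repeats it and adds CIWA-Ar: "e.g., TFLB score, CIWA-Ar score) will be summarized in terms of a difference and then included as a covariate". The optional wording in that paragraph, "possibly controlling for other subject-level covariates that remain constant (or nearly so) over the six months", reaches only the stable covariates such as age, sex and HCV genotype. TLFB is given as an example, but it is the named example both times. No model without these change covariates is described.

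Table 2 has a row for "Alcohol use (TLFB"), and its footnote a describes the tabulated variables as the primary outcomes. The Power paragraph claims "80% power for a 0.05-level test to detect any main effect, for either AUD or for HCV, of at least 0.51 SD", and says that the table "shows the smallest average change (between post- and pre-DAA therapy) among groups that would be of practical interest".

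Hypothesis 2.1 begins "Following DAA therapy and obtaining a sustained viral response (SVR") and then states that "participants without AUDs will show greater improvement in neuropsychiatric outcomes than participants with AUDs". Its contrast is therefore AUD+/HCV+ against AUD-/HCV+ among participants with SVR. It says nothing about equal drinking change.

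**The concern.** Baseline adjustment leaves the group question as it was. Adjusting for something that changes during follow-up, alongside the outcome, changes the question. Here the covariate is also strongly tied to group in the plan's own figures: Table 2's TLFB changes differ by 26.5 units between AUD+ and AUD-, and by 35 units within HCV+. The coefficient for AUD then compares people with and without AUD who changed their drinking by the same amount.

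Two things are at stake. The power statement may not describe the models that will be fitted. And a Hypothesis 2.1 result could be read as AUD limiting recovery when the two HCV+ groups improved almost equally and the gap came from the adjustment. The interaction is tested first in every model. If the covariate is in that step (implied, not stated), it also affects whether the interaction term is kept.

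**Working it through.** **Inputs from Table 2.** n = 30 per group; two-sided alpha 0.05 for main effects and 0.10 for the interaction. Mean changes are listed in the order AUD-/HCV-, AUD-/HCV+, AUD+/HCV-, AUD+/HCV+.
- TLFB: 0, -1, -18, -36; SD of change 18.9
- Attention: 3.5, 3.7, 1.2, 3.5; SD 2.25

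**Reproducing the plan, no covariate.** Standard errors in SD units, with noncentral t on 116 df:
- main effect: sqrt(4/120) = 0.183
- interaction: sqrt(4/30) = 0.365
- AUD within HCV+: sqrt(2/30) = 0.258

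Recomputed power for AUD/HCV/interaction, with the stated values in brackets:
- attention 0.855/0.855/0.815 (0.85/0.85/0.81)
- memory 0.903/0.903/0.774 (0.91/0.91/0.78)
- executive function 0.775/0.775/0.781 (0.78 each)
- BDI interaction 0.948 (0.94); fatigue interaction 0.828 (0.83)
- 0.51 SD main effect 0.79 (0.80)

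So these rows power plain contrasts of cell means. The FA row does not reproduce and is not used.

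**TLFB contrasts in SD units.**
- AUD main effect: -26.5/18.9 = -1.402
- HCV main effect: -9.5/18.9 = -0.503
- interaction: -17.0/18.9 = -0.899
- AUD within HCV+: -35/18.9 = -1.852

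**Adding TLFB change as a covariate** (115 df, SD units):
- adjusted contrast = contrast - r x TLFB contrast
- variance = (1 - r²) x (SE² + TLFB contrast²/116)

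Here r is assumed, from 0 to 0.4 in size. Its sign is set so that less drinking is beneficial: negative for cognitive scores, positive for BDI and fatigue.

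**r = 0.** AUD variance factor = 1 + (1.402²/116)/(4/120) = 1.51; it is 1.07 for HCV and 1.05 for the interaction. Power for 0.51 SD falls from 0.79 to 0.62. With three quarters of the TLFB gap it is 0.69, and with half the gap 0.74. The plan uses robust standard errors; a 3,000-run simulation with HC3 errors gave 0.80 without and 0.59 with the covariate.

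**Power by size of r, full Table 2 gap:**

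| Contrast | No covariate | 0 | 0.1 | 0.3 |
|---|---|---|---|---|
| Attention, AUD | 0.855 | 0.69 | 0.87 | 0.995 |
| Memory, AUD | 0.903 | 0.76 | 0.91 | 0.997 |
| Executive function, AUD | 0.775 | 0.60 | 0.81 | 0.99 |
| Fatigue, AUD | 0.99 | 0.94 | 0.83 | 0.41 |
| Attention, HCV | 0.855 | 0.83 | 0.76 | 0.61 |
| Cognitive interactions | 0.77-0.82 | 0.75-0.80 | 0.68-0.73 | 0.52-0.58 |

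**Shift in the estimates.** At r = -0.3:
- attention AUD main effect: -1.25 - 0.3 x 1.402 x 2.25 = -2.20
- attention, AUD within HCV+: -0.2 - 0.3 x 1.852 x 2.25 = -1.45 (-0.62 at size 0.1, -1.87 at 0.4)

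The other Hypothesis 2.1 contrasts at size 0.3:
- memory: -0.4 to -1.79
- executive function: -0.1 to -1.10
- fatigue: -0.2 to +0.15
- BDI: -7.5 to -5.28

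The chance of a significant attention contrast within HCV+ goes from 0.06 to 0.58.

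**The case against.** AUD status is not randomised. Veterans are recruited partly through the substance abuse treatment program, and in the preliminary Study 1 the AUD group cut its drinking markedly during a brief intervention. Drinking change may therefore reflect concurrent alcohol treatment, which would confound the plain contrast. Aim 2 names unhealthy drinking as well as AUD, so a comparison at equal drinking change may be closer to what the investigators want. This stands as a reason to keep the adjusted model. It does not make that model the one that Table 2 powers, nor the one that Hypothesis 2.1 describes.

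A reader might infer that AUD power is below the stated level whatever the correlation, and that enrolment must rise. The figures do not support this. The cognitive loss occurs only with r near 0; at a size of about 0.1 power is back to roughly the stated values. For these rows, power loss and a large shift are alternatives and cannot both occur.

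A reader might also infer that removing the covariate rescues Hypothesis 2.1. It does not. Table 2's plain contrasts within HCV+ are tiny for the cognitive rows (power 0.06 to 0.09), and for BDI and fatigue they run opposite to the hypothesis.

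Finally, Table 2's entries are minimally meaningful changes, so the TLFB gap may prove smaller.

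**Conclusion.** The point holds. As written, the models estimate AUD, HCV and interaction differences at equal concurrent drinking change, while Table 2 and Hypothesis 2.1 concern differences without that condition. Confidence is high for this reading of the text and for the r = 0 algebra, which rests on Table 2's TLFB gap and a common SD of 18.9.

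Confidence is moderate for the size and direction of any shift, because r is an assumption and Table 2's values are not forecasts. In that illustration, the results most exposed when r is not zero are the Hypothesis 2.1 contrast, HCV and interaction power for the cognitive rows, and AUD power for fatigue.

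CIWA-Ar change raises the same issue of principle, but the documents give no group values from which to size it. The finding does not extend to the imaging analyses, which are described without this covariate. It should be fixed before analysis.

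**What to change.** For the neuropsychiatric and laboratory outcomes:
- State a model without TLFB change and CIWA-Ar change as the primary analysis of AUD, HCV and AUD x HCV. Use it for the p > 0.10 interaction step as well.
- Name the Hypothesis 2.1 contrast: AUD+ against AUD- among HCV+ participants with SVR.
- Report the model with TLFB and CIWA-Ar change beside it, labelled as the association conditional on concurrent drinking, in support of Aim 2.
- Say that Table 2's power applies only to the model without these covariates.

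The cost is analysis-plan wording; no new data are needed and the current model is kept. The downside is that, in an observational cohort, the primary model does not separate AUD status from concurrent drinking change or alcohol treatment. The labelled adjusted model is there to address that.

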^aIn addition to the visits outlined in this table, Veterans receiving DAA therapy participate in two standard, follow-up clinic appointments at weeks 4 and 8 (typically 15-20 min appointments). Note: *The follow-up clinic is a large multidisciplinary clinic comprised of doctors, fellows, nurse practitioners, liver clinic pharmacist and pharmacy students. Patients do not usually see the same clinician at the follow-up appointments that they saw at the start appointment. In addition, approximately 50% of individuals started on DAA therapy are followed in the pharmacist phone clinic, and the week 4 and 8 appointments are by phone (~10 min calls).* The potential impact of these additional interactions on study outcomes is discussed in Expected outcomes and alternative considerations. ^bClinical research staff will check-in with participants (phone contact) to assess general well-being, complete the TLFB (Sobell et al., 1996), and confirm schedules for follow-up visits.

^cParticipants will be paid \$125 for the baseline visits (\$75 for visit 1 [clinical interview, neuropsychiatric assessment, specimen collection] and \$50 for visit 2 [specimen collection, neuroimaging evaluation]). Subjects who participate in the 6-month follow-up visits will receive an additional \$125 (\$75 for visit 3 [neuropsychiatric assessment, specimen collection] and \$50 for visit 4 [specimen collection, neuroimaging evaluation]). In sum, subjects can earn \$250 total if they complete all of the scheduled visits.

Enrollment procedures. Prior to enrollment, a phone screening will be conducted by study staff to ensure that Veterans are interested in participating and meet eligibility criteria. Following screening, interested Veterans will be scheduled for a first study visit to review consent materials either in person at the VAPORHCS, by telephone, or VA approved teleconferencing software (i.e., VA Video Connect [VVC] or non-public facing technologies [i.e., Cisco WebEx, Skype for Business, Zoom for Healthcare, Doxy.me]).

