Expected outcomes and alternative considerations. Results are expected to determine the extent of improvement in CNS function (including neuropsychiatric outcomes) that is gained by successful completion of DAA therapy and whether or not co-morbid AUDs affect HCV treatment outcomes. Our hypotheses would be supported by finding improved CNS function following successful completion of DAA therapy (*i.e.*, obtaining an SVR), including: i) increased FA in the tracts that previously connected regions between which there was decreased functional connectivity, ii) improved functional connectivity, iii) reduced impulsivity, and iv) improved cognitive abilities. Following DAA therapy, these changes in CNS function will be associated with reduced peripheral immune activation. Individuals with active AUDs and HCV may show attenuated benefits in CNS function and immune response, post-DAA therapy. In participants with HCV and co-morbid AUDs, cumulative disruptions in cerebral connectivity that result from anatomical disruptions may contribute to persistent cognitive deficits and elevated inflammatory profiles. Alternatively, it is possible that floor effects for some of the variables (e.g., BDI-II scores) may limit our ability to detect significant improvements. However, cognitive performance benefits have been reported following IFN-based therapy for HCV (Kraus et al., 2013, Kuhn et al., 2017), and we have observed improvements in depression and fatigue in patients who obtained SVR (Huckans et al., 2015). It is also possible that differences in the number of DAA therapy provider visits between participants in the HCV+ and HCV- groups may affect neuropsychiatric outcome variables (e.g., alcohol use behavior). To assess the impact of this potential confound, we plan to include that characteristic as an extra covariate. Because CNS recovery may continue beyond the SVR assessment timepoint, patients who agree to participate in the study will be asked to allow our research team permission (via the informed consent process) to contact them for future follow-up investigation, which is beyond the scope of this current protocol. We also considered the potential concern that there may be a lack of research participants with HCV (given the pace at which the VA is treating HCV); however, estimates indicate that by 2020, there will still be ~560,000 adults with HCV in the US (Chhatwal et al., 2016).

Table 3. Project timeline

Year 1	Year 2	Year 3	Year 4

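### Adjusting the four-group models for a raw count of DAA provider contacts makes the HCV coefficient an extrapolation to zero contacts and removes its stated 80% power

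*Combined protocol and SAP*

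**What the plan says.** Under Statistical analyses and power (Neuropsychiatric and laboratory measures), change scores are compared across the four AUD/HCV groups with general linear models and sandwich variances. Other fixed covariates are optional, the wording being "possibly controlling for other subject-level covariates that remain constant (or nearly so) over the six months (e.g., age, sex, HCV genotype"). The contact count is not optional: "Number of DAA therapy provider contacts will be included as an extra covariate that counts total contacts". If the AUD × HCV interaction is kept, the follow-up is "effect of HCV separately characterized for those with and then without AUD".

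Expected outcomes and alternative considerations gives the reason, namely that "differences in the number of DAA therapy provider visits between participants in the HCV+ and HCV- groups may affect neuropsychiatric outcome variables", and the remedy: "To assess the impact of this potential confound, we plan to include that characteristic as an extra covariate".

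Table 1, footnote a, shows where the contacts come from: "Veterans receiving DAA therapy participate in two standard, follow-up clinic appointments at weeks 4 and 8". It adds that about half of "individuals started on DAA therapy are followed in the pharmacist phone clinic, and the week 4 and 8 appointments are by phone".

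The Power paragraph claims "80% power for a 0.05-level test to detect any main effect, for either AUD or for HCV, of at least 0.51 SD in size". Neither that paragraph nor Table 2 mentions covariate adjustment. The plan specifies no coding or centring of the count, no model restricted to HCV+, and no primary model with or without the count.

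**The concern.** A covariate can adjust a group comparison only where the groups overlap on it. Here the count is zero for everyone without HCV and should cluster around the scheduled number in those with HCV. Phone follow-up keeps the week 4 and week 8 schedule, so it changes the mode and length of a contact but not the total.

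The slope on contacts is then learned entirely within HCV+. The HCV coefficient is obtained by running that slope back to zero contacts, where there are few or no treated patients. Sandwich variances do not cure this collinearity.

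The four-group model is the only analysis specified for these outcomes, and its HCV term is the only contrast of change in treated HCV+ participants with change in HCV- participants. A null result could come from the collinearity alone and be read as no benefit of viral clearance.

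**Working it through.** **Inputs from the protocol.** 30 per group, so 60 HCV+ and 60 HCV-; two-sided 0.05 for main effects; 0.51 SD; Table 2 effects and SDs. **Assumptions.** Count is 0 in HCV-, with mean m and SD s in HCV+; contacts are balanced by AUD; the contact slope is zero in the power figures.

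**1. Reproduce the stated power.** Without the count, SE = √(1/60 + 1/60) = 0.183 SD, and 0.51/0.183 = 2.79. Power is 0.80 by the normal approximation and 0.79 by the noncentral t (116 df). The claim therefore rests on a plain 60 versus 60 comparison.

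**2. Add the raw count.** The HCV coefficient is the difference in mean change minus slope × m, and the slope comes from HCV+ only. Hence

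Var = σ²[1/60 + 1/60 + m²/(60s²)] = σ²(2/60)[1 + m²/(2s²)].

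If s = 0, the design matrix (intercept, AUD, HCV, AUD × HCV, count) has rank 4 of 5 columns. HCV and contacts cannot then be separated, although AUD and AUD × HCV still can.

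**3. Put in plausible counts.** The protocol gives neither m nor s. Suppose only the two scheduled follow-ups count and each is attended independently with probability p. Then m = 2p and s² = 2p(1−p), so m²/(2s²) = p/(1−p) and the inflation is 1/(1−p).

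| p | Inflation | Power at 0.51 SD | Effect detectable with 80% power (SD) |
|---|---|---|---|
| no count | 1 | 0.79 | 0.52 |
| 0.5 | 2 | 0.50 | 0.73 |
| 0.7 | 3.3 | 0.33 | 0.94 |
| 0.8 | 5 | 0.24 | 1.15 |
| 0.9 | 10 | 0.14 | 1.63 |

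If a start visit is always counted too, the inflation is 1 + (1+2p)²/(4p(1−p)): 11.6 at p = 0.8 (power 0.13) and 22.8 at p = 0.9 (power 0.09).

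Free choices of m and s:
- m = 3 to 4 with s = 0.5 to 1.5: power 0.08 to 0.36.
- m = 2 with s = 1.5 to 2 (many unscheduled contacts): inflation 1.89 to 1.5, power 0.52 to 0.62.

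**4. Table 2 outcomes, HCV main effect.** Inflations of 3 and 10 are illustrative.

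| Outcome | Stated power | Inflation 3 | Inflation 10 |
|---|---|---|---|
| Attention | 0.85 | 0.41 | 0.16 |
| Memory | 0.91 | 0.47 | 0.18 |
| Executive function | 0.78 | 0.35 | 0.14 |
| Depression (BDI) | 0.99 | 1.00 | 0.72 |
| Fatigue (FSS) | 0.99 | 0.98 | 0.59 |
| Immune factors | 0.99 | 1.00 | 0.91 |

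**5. HCV effect within an AUD level.** With one common slope, Var = σ²[1/30 + 1/30 + m²/(60s²)] = σ²(2/30)[1 + m²/(4s²)]. These effects are inflated too, but by less.

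**6. Simulation with sandwich (HC3) errors**, N = 120, 4,000 runs. HCV power at 0.51 SD:

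| Contacts in HCV+ | No count | Raw count | Count centred within HCV+ |
|---|---|---|---|
| Two visits, p = 0.5 | 0.78 | 0.49 | 0.78 |
| Two visits, p = 0.8 | 0.78 | 0.22 | 0.78 |
| Two visits, p = 0.9 | 0.79 | 0.15 | 0.78 |
| Mean 2, SD 2 (negative binomial) | 0.77 | 0.59 | 0.77 |

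With the raw count, power is 0.77–0.79 for AUD at 0.51 SD and 0.78–0.80 for the interaction at 0.91 SD (level 0.10).

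**The case against.** *Visits or contacts.* The rationale speaks of visits. If only in-person visits count, about half of HCV+ would sit at zero, the groups would overlap, and extrapolation would not be the right word. The analysis section says total contacts, which favours the other reading without settling it. Even with counts of 0 or 2 split evenly (m = s = 1), inflation is 1.5 and power about 0.62 (0.61 simulated). The milder scenarios above also include treated patients at zero; the severe ones assume nearly constant counts.

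*A sensitivity analysis may be intended.* The design overview describes the model without contacts, and the rationale speaks of assessing the impact of a confound. That reading is possible, but the analysis section makes inclusion firm and no primary model is named.

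*Different estimands.* This point stands. The models without the count, or with it centred, test therapy plus contact as a package. With no true HCV effect and a contact slope of 0.3 SD (p = 0.8), they declare HCV significant in about 73% of simulated runs, against 6–7% with the raw count. The recovered power is power for the package, so the plan must say so.

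*Limited reach.* Aim 2 rests on terms that are nearly intact. Hypotheses 1.1 and 1.3 are worded as change from baseline, large planned effects survive moderate inflation, and the HCV main effect is read only if the interaction is dropped. All true, but the HCV effects within AUD levels are inflated as well, and no other analysis is specified for these outcomes.

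**Conclusion.** The concern holds, and the plan should be changed. As written, the HCV term is either not estimable (equal counts in all treated patients) or estimated with inflated variance at a point with little or no treated data. Every contact distribution examined brought power at 0.51 SD below the stated 80%, from about 0.62 for very dispersed counts to about 0.08 for nearly constant ones. Effects near 0.5 to 0.6 SD, including all three cognitive domains, suffer most.

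Confidence is high on the direction. The size is a range, because the contact distribution is not documented and zero contacts in HCV- is inferred. The loss would be offset only if contacts explained much of the residual variance: 1 − 1/inflation, or 33% when s = m and 67% when s = m/2. The finding covers the HCV terms in the neuropsychiatric and laboratory models; the connectivity t-tests are outside it.

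**What to change.** - Remove the raw contact count from the four-group models. Alternatively, enter it as the deviation from the HCV+ mean, with 0 for all HCV- participants. The second option is the same fitted model, but its HCV coefficient is the contrast at average contacts and keeps about 77–79% power at 0.51 SD. Centring on the overall mean would not help.
- State which model is primary and what its HCV coefficient means.
- Examine contacts as a sensitivity analysis within the 60 HCV+ participants, recording mode (phone or clinic) as well as number, and define which contacts count.
- State that this design cannot separate the HCV/DAA effect from clinic contact; centring does not remove that confound.
- Use HCV genotype only in analyses restricted to HCV+, since it is undefined in HCV-.

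The cost is wording, plus one recorded item if contact mode is wanted. The sponsor gives up a claim to have adjusted the HCV effect for contacts, which the data could not support.
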